3.2. Part 1 Study Design

Part 1 is an open-label, lead-in, dose and age escalation phase evaluating VXA-COV2-1.1-S oral vaccine in healthy adult participants with repeat dose administration; this part of the study will enroll a total of approximately 72 subjects across 2 cohorts. Cohort 1 will evaluate 36 total healthy adult participants that are naïve (no prior vaccination against SARS-CoV-2 infection and no history of prior COVID-19 or SARS-CoV-2 infection) across 3 groups of 12 subjects each, encompassing 2 age groups and 2 dose levels. Cohort 2 will evaluate 36 healthy adult participants who have no history of prior COVID-19 or SARS-CoV-2 infection and have received 2 doses of an EUA or FDA approved COVID-19 mRNA vaccine across 3 groups of 12 subjects each, encompassing 2 age groups and 2 dose levels. Enrollment will be performed in a sequential manner with at least 12 subjects in the younger age group (18-55 years) completing within their dose level, prior to enrollment of the older age group (56-75 years) at that dosage.

- Cohort 1- Healthy adults who are naïve (no prior vaccinations against COVID-19 and no history of COVID-19) and are at low risk of developing severe COVID-19 upon potential infection with SARS-CoV-2
- Cohort 2- Healthy adults who are prior vaccinated (have received two doses of an EUA or FDA approved mRNA COVID-19 vaccine at least 6 months prior to enrollment [Day 1], no history of COVID-19 and are at low risk of developing severe COVID-19 upon potential infection with SARS-CoV-2

The study includes a Screening Period, Active Period and a Safety Follow-up Period. Study assessments will be conducted as shown in the Schedule of Activities (SoA) in Section 1.2 (Table 3).

After signing an informed consent, participants will undergo screening assessments to determine study eligibility over a 30-day Screening Period.

3.2.1. Part 1: Enrollment and Initial Vaccination

On Day 1, eligible participants will be enrolled sequentially to receive their 1st oral vaccination according to their assigned treatment group as specified in Table 1.

Population	Cohort	VXA-CoV2-1.1-S Dose Levels*	Age (years)	No of Doses	No. of Participants
Naive	1a	Low Dose: $1x10^{10}$ I.U. $\pm 0.5 \log$	18 - 55	2	12
Prior vaccinated	2a	Low Dose: $1x10^{10}$ I.U. $\pm 0.5 \log$	18 - 55	2	12
IDMC Data Review ¹					
Naive	1b	High Dose: 1x10 ¹¹ I.U. ±0.5 log	18 - 55	2	12
Naive	1c	Low Dose: $1x10^{10}$ I.U. $\pm 0.5 \log$	56 - 75	2	12
Prior vaccinated	2b	High Dose: 1×10^{11} I.U. $\pm 0.5 \log$	18 - 55	2	12
Prior vaccinated	2c	Low Dose: $1x10^{10}$ I.U. $\pm 0.5 \log$	56 - 75	2	12
	IDMC Data Review ²				

* Multiple tablets may be administered to deliver the full intended dose.

[†] Doses will be administered on Day 1 and Week 4.

¹ IDMC to review safety data through Week 1 for 12 subjects in a before enrollment will begin in b or c.

² IDMC to review safety data for all subjects within each age group and initial immunogenicity data from Part 1 to make recommendations to Sponsor on dose selection for randomized, placebo-controlled phase, before enrollment begins in Part 2

Cohorts 1 and 2 (naïve and prior vaccinated subjects, respectively) will enroll in parallel. The IDMC may review safety data for the subgroups within each of these two cohorts separately if the enrollment rates between the two cohorts vary.

During the Active Period, participants will record daily symptoms of reactogenicity for 1 week post each vaccination, administered on Day 1 and Week 4, using a Solicited Symptom Diary. They will return to the site at 1 and 4 weeks following each vaccination, as specified in the SoA, to have safety assessments and samples collected for evaluation of immunogenicity. Post completion of the Week 1 visit by all subjects in a specified cohort, as detailed in

Table 1, the IDMC will review Day 1 to Week 1 safety data and make recommendations as to whether to proceed to the next cohort(s). Upon completion of enrollment in Part 1, the IDMC will review safety and preliminary immunogenicity data from all cohorts and make recommendations to the Sponsor on the VXA-CoV2-1.1-S dose level to evaluate in Part 2. A summary of Part 1 safety and immunogenicity data with the intended dose for Part 2 will be submitted to FDA for review and concurrence prior to initiation of enrollment in Part 2.

3.2.2. Part 1: Eligibility for Second Vaccination

At the Week 4 visit participants will have safety assessments to evaluate suitability to receive the second vaccination including physical exam, vital signs, pregnancy test (female participants), SARS-CoV-2 rapid molecular test, and assessment of adverse events and new concomitant medication usage. Participants meeting any of the following exclusion criteria will not be eligible to receive their second vaccine administration:

Exclusion Criteria for Second Vaccine Dose:

• Positive pregnancy test at Day 29 (female participants),

Version 5.0

- Occurrence of any possibly, probably or definitely treatment-related Grade 3 or 4 AE or SAE following the initial vaccination
- Occurrence of any Grade 3 or 4 AE or SAE following the initial vaccination without plausible alternative explanation
- Presence of acute illness or significant new medical condition including positive SARS-COV-2 rapid molecular test prior to dosing

Participants deemed ineligible due to presence of acute illness or new medical condition may be re-assessed during the visit window (+7 days), and if the condition resolves, may receive their second vaccination within 1 week of their scheduled Week 4 Visit. In such situations the Principal Investigator must contact the study Medical Monitor and gain consensus on the decision to continue participant with study vaccinations prior to administration of the second dose.

Upon completion of the study Active Period (Week 8 Visit) participants will enter the Safety Follow-up Period and be monitored for SAEs, MAAEs and for exposure to and/or symptomatic COVID-19, including the potential for VAED, through the Month 13/End of Study (EOS). In addition, these participants will be evaluated for immunogenicity as specified in the SoA (Table 3). During the Safety Follow-up Period participants will return to the site at Months 7 and 13 for safety monitoring and collection of samples for evaluation of immunogenicity; they will also be contacted by phone monthly between site visits to query for safety and exposure to and/or symptomatic COVID-19.

Any participant who discontinues study drug early (does not receive the second dose) will enter the Safety Follow-up Period a month earlier at Week 4 and will be monitored for safety and exposure to and/or symptomatic COVID-19 as described above, and complete immunogenicity assessments through EOS per the SoA (Table 3).

Any participant reporting COVID-19 like illness or exposure to COVID-19 during the study will be asked to return to the site for an unscheduled visit to test for SARS-CoV-2 infection. Participants with confirmed SARS-CoV-2 infection, at any time during the study period will be asked to provide a nasal swab sample every two days after their confirmatory COVID-19 test, until they test negative, to monitor for duration of infection. The duration of q2day testing post confirmed SARS-CoV-2 infection should end after 10 days if still testing positive at that time. Any FDA Authorized rapid molecular test (e.g. LUCIRA COVID-19 Test) can be used for home or on-site testing for monitoring COVID-19 infection. They will also be monitored for clinical disease severity (see Section 7.1.1, Table 6) and outcome. The participant will be counseled to notify their Primary Care Physician of their positive SARS-CoV-2 status and seek medical care should they become symptomatic.

An Independent Data Monitoring Committee (IDMC) will provide safety oversight throughout the duration of the study. If the protocol halting rules are met at any time during the study (refer to Section 6.1.1 for Part 1 and Section 6.1.2 for Part 2), enrollment and dosing will be suspended pending a full IDMC review (Section 8.5.2). The Sponsor's Medical Monitor(s) (or designees) will perform safety oversight (Section 8.5.1).

3.2.3. Part 1 Scientific Rationale for Study Design

Part 1 is an open-label, lead-in, dose and age escalation lead-in phase to allow assessing the following parameters in subjects that are naïve to prior vaccination and COVID-19 and those who have received two prior vaccinations against SARS-CoV-2 with an EUA or FDA approved mRNA vaccine:

- Collection of additional safety data in young adults. Though doses as high as two times $1x10^{11}$ IU \pm 0.5 log have been tested with other oral vaccines using the VAASTTM platform, in the Phase 1 study with VXA-CoV2-1 (S and N protein construct), the highest dose tested was $5x10^{10}$ IU \pm 0.5 log due to limited drug product availability. Safety of VXA-CoV2-1.1-S will be evaluated at two dose levels in Part 1 to allow optimal dose selection for the larger, placebo-controlled phase in Part 2; doses to be tested will include $1x10^{10}$ IU \pm 0.5 log (low dose) and $1x10^{11}$ IU \pm 0.5 log (high dose).
- Collection of safety data in older healthy adults with repeat dose administration at the lower dose level . Safety data collected in Part 1 will inform inclusion of this population in Part 2.
- Collection of preliminary data on the immunogenicity of VXA-CoV2-1.1-S vaccine at 2 potentially clinically active doses, 1×10^{10} IU \pm 0.5 log (low dose) and 1×10^{11} IU \pm 0.5 log (high dose). Based on early (Day 8) immunogenicity data from Part 1, the dose level for Part 2 will be selected.

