IDMC = Independent Data Monitoring Committee.

¹ IDMC to review safety data through Week 1 for 12 subjects in group a before enrollment will begin in b and c.

² IDMC to review safety data for all subjects within each age group and initial immunogenicity data from Part 1, to make recommendations on dose selection for randomized, placebo-controlled phase, before enrollment begins in Part 2.

Cohorts 1 and 2 (naïve and prior vaccinated subjects, respectively) will enroll in parallel, and the IDMC may review safety data for the two Cohorts separately if the enrollment rates between the two groups vary.

After signing an informed consent, participants will undergo screening assessments to determine study eligibility over a 30-day Screening Period.

On Day 1, eligible participants will be enrolled sequentially to receive their 1st oral vaccination according to their assigned treatment group as specified in Table 1.

During the Active Period, participants will record daily symptoms of reactogenicity for 1 week post each vaccination, administered on Day 1 and Week 4, using a Solicited Symptom Diary. They will return to the site at 1 and 4 weeks following each vaccination, as specified in the SoA, to have safety assessments and samples collected for evaluation of immunogenicity. Post completion of the Week 1 visit by all subjects in a specified cohort, as detailed in

Table 1, the Independent Data Monitoring Committee (IDMC) will review Day 1 to Week 1 safety data and make recommendations as to whether to proceed to the next cohort(s). Upon completion of active portion of Part 1, the IDMC will review safety and preliminary immunogenicity data from all cohorts and make recommendations to the Sponsor on the VXA-CoV2-1.1-S dose level to evaluate in Part 2. A summary of safety and immunogenicity data with the intended dose for Part 2 will be submitted to FDA for review and concurrence prior to initiation of enrollment in Part 2.

At the Week 4 visit participants will have safety assessments to evaluate suitability to receive the second vaccination as outlined in Section 3.2.2. Participants with any of the following conditions will not be eligible to receive a second vaccine dose:

- Positive pregnancy test at Day 29 (female participants),
- Occurrence of any possibly, probably or definitely treatment-related Grade 3 or 4 AE or SAE following the initial vaccination

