7.1.2. Immunogenicity

Samples will be collected from all participants for immunogenicity assessment according to the time points specified in the SoA (Section 1.2; Table 3 and Table 4). The following immunoassays will be performed:

Key immunogenicity assessments:

Part 1:

- SARS-CoV2-specific IgG/IgA by MSD (Serum)
- Neutralizing antibody titers to SARS-CoV-2 (Serum)

Part 2:

- SARS-CoV2-specific IgG/IgA by MSD (Serum)
- Neutralizing antibody titers to SARS-CoV-2 (Serum)

Additional Immunogenicity Assessments:

Part 1:

- T cell responses by intracellular cytokine cytometry (ICC)
- Antigen S-specific IgA (Nasal Swabs)

- Antigen S-specific IgA (Saliva)
- Anti Ad5 antibodies (optional), (Serum)

Part 2:

- Antigen S-specific IgA (Nasal Swabs)
- Antigen S-specific IgA (Saliva)

Additional exploratory immunoassays may also be run to further characterize the immune response of the VXA-CoV2-1.1-S vaccine. Sample collection, processing and shipping details are provided within the General and Immunogenicity Laboratory Manuals.

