	Geometric mean titers/concentrations (GMTs/GMCs) of SARS-CoV-2 neutralizing titers, S-binding IgG level, , and S-binding IgA levels serum, nasal and saliva), GMTs/GMCs and 2-sided 95% CIs and other reported antigens will be provided for by treatment group at the following time points:
	• Day 1, Week 4, Week 8, Optional (Month 7, and Month 13)
	• Geometric means will be calculated as the mean of the assay results after making the logarithm transformation and then exponentiating the mean to express results on the original scale. Two-sided 95% CIs will be obtained by taking natural log transforms of concentrations/titers, calculating the 95% CI with reference to the t-distribution, and then exponentiating the confidence limits.
	The geometric mean fold rise (GMFR) of SARS-CoV-2 neutralizing titers, S-binding IgG level, and S-binding IgA level. For SARS-CoV-2 neutralizing titers, S-binding IgG levels, and S-binding IgA levels, the GMFRs and 2-sided 95% CIs will be provided by treatment group at the following time points:
	• Week 4, Week 8, Optional (Month 7, and Month 13)
	GMFRs will be limited to participants with non-missing values prior to the first dose and at the postvaccination time point. The GMFR will be calculated as the mean of the difference of logarithmically transformed assay results (later time point – earlier time point) and exponentiating the mean. The associated 2-sided CIs will be obtained by calculating CIs using Student's t-distribution for the mean difference of the logarithmically transformed assay results and exponentiating the confidence limits.

Vaxart, l	Inc.
-----------	------

	Percentage of participants with ≥4-fold rise (or other assessments as per the SAP) in SARS-CoV-2 neutralizing titers, S1-binding IgG level, and RBD-binding IgG level will be summarized by treatment group at the following timepoints.
	• Week 4, Week 8, Optional (Month 7, and Month 13)
	For all the immunogenicity endpoints, the analysis will be based on the Dose 1 and Dose 2 evaluable immunogenicity populations. An additional analysis will be performed based on the all-available immunogenicity populations if there is a large enough difference in sample size between the all-available immunogenicity populations and the evaluable immunogenicity populations. Participants will be summarized according to the vaccine group to which they were randomized.
	Additional immunogenicity data will be assessed as per the SAP. Missing serology data will not be imputed.

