8.4. Interim Analysis

During Part 1, following completion of the Active Period by all Cohorts, the database will be cleaned and locked.

During Part 2, an interim analysis will occur at 18* confirmed cases of SARS-CoV2 infection. In addition to efficacy, this interim analysis would also include evaluation of safety and immunogenicity through Week 8. If 18 confirmed cases are not identified, the study will be considered complete at 6 months post last vaccination and the database will be locked and unblinded. At this time the efficacy analysis will be conducted, O'Brien-Fleming methods will be used for halting rules (O'Brien, 1979):

- If P = 0.003 at the interim analysis, the study may be stopped for overwhelming efficacy.
- If the study completes as planned (i.e., 6 months post last vaccination), it will be determined to be successful if $P \le 0.05$.

*VE null = 30% (since that is lower bound from the FDA) and VE_Alt = 80% and ARU = 0.05 we get p0 = 0.41 and p1 = 0.17 which gives a total target number of events of around 31 (with ~5 from vaccine group and 26 in placebo so if we add in the other dose then looking at around 36 total events) using POT0 if we simplify down to one primary dose vs placebo calculation. So interim analysis at 1/2 * 36 = 18 events (or 6 months post last vaccination, whichever is first) (Follmann, 2020).

The SAP will describe the planned interim analysis in greater detail.

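### Section 3.2.3 selects the Part 2 dose on Day 8 immunogenicity data, when neither key antibody endpoint is sampled, and Section 3.2.1 times the dose review earlier than the Synopsis does

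*Combined protocol and SAP*

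**What the plan says.** **Basis for the dose choice.** Section 3.2.3 says: "Based on early (Day 8) immunogenicity data from Part 1, the dose level for Part 2 will be selected". Section 2.1.1 refers to early immunogenicity and safety data from Part 1 without naming a day.

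**Timing of the dose review.** The Synopsis (Part 1 Design) says: "Upon completion of active portion of Part 1, the IDMC will review safety and preliminary immunogenicity data from all cohorts". Section 3.2.1 has nearly the same sentence with a different trigger: "Upon completion of enrollment in Part 1, the IDMC will review safety and preliminary immunogenicity data from all cohorts". Section 8.4 says: "During Part 1, following completion of the Active Period by all Cohorts, the database will be cleaned and locked".

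**Order of enrollment.** Footnote 1 to the Part 1 table in the Synopsis says: "IDMC to review safety data through Week 1 for 12 subjects in group a before enrollment will begin in b and c". Group a is the low dose at ages 18-55, group b the high dose at ages 18-55, and group c the low dose at ages 56-75.

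**Endpoints.** Sections 3.1 and 7.1.2 name two key Part 1 immunogenicity endpoints: serum SARS-CoV-2-specific IgG/IgA by MSD, and serum neutralizing antibody titers. T-cell responses by ICC are listed as an additional endpoint.

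**The concern.** The Part 1 review fixes the single dose that 400 participants receive in the active arm of Part 2. The basis written in Section 3.2.3 leaves out both endpoints that the protocol itself ranks as key. It also precedes Dose 2, although Part 2 tests a two-dose schedule and counts efficacy from 7 days after Dose 2.

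The second problem is that the review has two triggers. A review held when enrollment completes would compare dose groups with unequal follow-up, because the high-dose group cannot start until the low-dose group's Week 1 safety data have been reviewed. Late-enrolled high-dose participants would contribute baseline samples only. The Synopsis timing avoids this, but nothing in the protocol says which text governs.

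**Working it through.** **1. What is sampled at Day 8.** The Part 1 immunogenicity rows of Table 3, on nominal visit days:

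| Assessment | Rank (Sections 3.1, 7.1.2) | D1 | D8 | D29 | D36 | D57 | Months 7 and 13 |
|---|---|---|---|---|---|---|---|
| Serum IgG/IgA | key | X | – | X | – | X | X |
| Serum neutralizing antibody | key | X | – | X | – | X | X |
| T-cell ICC | additional | X | X | X | X | – | – |
| Nasal IgA, saliva IgA | additional | X | – | X | – | X | X |
| Anti-Ad5 (optional) | additional | X | – | X | – | X | – |
| Fixed whole blood | exploratory assays | X | X | X | X | – | – |

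Key endpoints sampled at Day 8: 0 of 2. The antibody analysis time points in Section 8.3.1 agree with the table: Day 1, Week 4, Week 8 and optional Months 7 and 13, with no Day 8.

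- First post-dose serum: 29 − 8 = 21 days after Day 8, at the visit where Dose 2 is given.
- First serum after Dose 2: 57 − 8 = 49 days after Day 8.

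The other Day 8 or Week 1 reviews (Synopsis, Sections 2.1 and 3.2.1) concern safety data for moving between groups, so they do not explain the Section 3.2.3 sentence.

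**2. Gap between the two review triggers.** Enrollment completes on the last participant's Day 1. The active portion completes at that participant's Week 8 visit, Day 57. The gap is 57 − 1 = 56 days.

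**3. Antibody data available at completion of enrollment.** The protocol gives no accrual times, so these are assumptions:

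- Each group of 12 enrolls evenly over T weeks, with participant i entering at iT/12.
- Groups b and c start together, 1 week after the last group a participant is dosed, with no IDMC delay.
- The data cut is the day the last b/c participant is dosed, at 2T + 1 weeks.
- Naive and prior-vaccinated cohorts run in parallel, so counts are doubled (24 per dose at ages 18-55).

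A sample due w weeks after Dose 1 exists if:

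- group a (low dose): iT/12 ≤ 2T + 1 − w
- group b (high dose): (T + 1) + iT/12 ≤ 2T + 1 − w, that is iT/12 ≤ T − w

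Examples:

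- T = 4, w = 8, group a: i/3 ≤ 1, so i ≤ 3, giving 2 × 3 = 6.
- T = 12, w = 8, group b: i ≤ 4, giving 2 × 4 = 8.

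| T (weeks) | Week 4 serum, low dose | Week 4 serum, high dose | Week 8 serum, low dose | Week 8 serum, high dose |
|---|---|---|---|---|
| 4 | 24 of 24 | 0 of 24 | 6 of 24 | 0 of 24 |
| 8 | 24 of 24 | 12 of 24 | 24 of 24 | 0 of 24 |
| 12 | 24 of 24 | 16 of 24 | 24 of 24 | 8 of 24 |
| 24 | 24 of 24 | 20 of 24 | 24 of 24 | 16 of 24 |

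The counts ignore assay turnaround.

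**The case against.** **Day 8 is not empty.** T-cell ICC is a listed secondary endpoint and the vaccine is meant to raise T-cell as well as antibody responses. No text says that only key endpoints may drive the dose, and Section 3.2.3 does not say that Day 8 data are the sole basis. This stands as far as it goes: some immunogenicity data exist at Day 8, and safety data also inform the choice. It does not explain why the only time point named for the decision excludes both key endpoints and everything after Dose 2.

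**Other safeguards apply.** The IDMC only recommends, and FDA must concur on a summary of Part 1 safety and immunogenicity data before Part 2 enrolls. The Synopsis and Section 8.4 agree on the later timing, so the text in Sections 3.2.1 and 3.2.3 may simply not have been harmonized. That is plausible and limits the practical risk. But none of these texts says which immunogenicity time points the review or the summary must contain.

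**Section 3.2.1 may mark the start of the review step, not a data cut.** That reading is possible, since the same sentence asks for data from all cohorts. The wording does not settle it.

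**The accrual counts are assumptions.** This is correct. Slower accrual narrows the gap, as the 24-week row shows, and the protocol itself describes naive participants as increasingly hard to recruit. The counts also pool the two cohorts, which the IDMC may review separately. The direction does not depend on T, because group b always starts after group a.

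**Conclusion.** Both parts of the concern hold. As written, Section 3.2.3 bases the Part 2 dose on a time point with 0 of 2 key antibody endpoints, 21 days before the first post-dose serum and 49 days before the first serum after Dose 2. Section 3.2.1 and the Synopsis set dose-review triggers 56 days apart for the last participant enrolled. These figures come directly from the protocol and use nominal visit days.

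The imbalance in antibody data between doses applies only if the review uses a data cut at completion of enrollment, and its size depends on the assumed accrual. A review run on the Synopsis timing would have Week 4 and Week 8 antibody data on both doses. The point should be corrected because it concerns a stated decision rule; it does not show that the Part 1 sampling is inadequate.

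**What to change.** - **Section 3.2.3:** replace the Day 8 basis with safety and immunogenicity data through Week 8, naming serum IgG/IgA and neutralizing titers, and keep Day 8 T-cell data as supportive.
- **Section 3.2.1:** change the trigger for the IDMC dose review from the end of enrollment to the end of the active portion, matching the Synopsis and the Section 8.4 lock.

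The cost is wording in two sections. Table 3 already collects the samples, no visits are added, and there is no delay beyond the timing the Synopsis already sets.
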